8.2.4. Safety Analyses

All safety analyses will be summarized based on the safety analysis set.

8.2.4.1. Adverse Events

Overall Summary of AEs

An AE will be regarded as treatment-emergent, if

- it occurs on the day of or after the first dose of either napabucasin or a combination drug and up to 30 days after the last dose of any study drug; or
- it occurs prior to first dose date of either napabucasin or a combination drug and worsens in severity on therapy and up to 30 days after the last dose of study drug.

Adverse events will be coded by SOC and PT using the MedDRA version 18.0 prior to the analysis. The severity of AEs will be graded by the investigator using CTCAE Version 4.0. The verbatim term will be included in the AE listings.

An overview of treatment-emergent adverse events (TEAEs) will be provided. The number and percentage of patients will be summarized for:

- Patients with at least one TEAE
- Patients with TEAE of CTCAE Grade 3 or higher
- Patients with serious TEAE
- Patients with napabucasin related TEAE
- Patients with napabucasin related TEAE of CTCAE Grade 3 or higher
- Patients with Cetuximab related TEAE
- Patients with Cetuximab related TEAE of CTCAE Grade 3 or higher
- Patients with Panitumumab related TEAE
- Patients with Panitumumab related TEAE of CTCAE Grade 3 or higher
- Patients with Capecitabine related TEAE
- Patients with Capecitabine related TEAE of CTCAE Grade 3 or higher
- Patients with napabucasin related serious TEAE
- Patients with napabucasin related serious TEAE of CTCAE Grade 3 or higher
- Patients with Cetuximab related serious TEAE
- Patients with Cetuximab related serious TEAE of CTCAE Grade 3 or higher
- Patients with Panitumumab related serious TEAE
- Patients with Panitumumab related serious TEAE of CTCAE Grade 3 or higher
- Patients with Capecitabine related serious TEAE
- Patients with Capecitabine related serious TEAE of CTCAE Grade 3 or higher
- TEAE as the primary reason leading to end of study

Summary of AEs by System Organ Class and Preferred Term

The number and percentage of patients with AEs by SOC and PT and maximum CTCAE grade will be summarized. A summary of TEAEs of CTCAE grade 3 or higher (Grade 3, 4, 5) will be presented by SOC and PT and maximum CTCAE grade. A summary of TEAEs by PT and maximum grade will be presented in the descending order of frequency counts for all grades.

Treatment Related TEAE

AEs reported with a relationship to a treatment considered by the investigator to be 'possible', 'probable' or 'definite' will be considered "Related" to BBI608 or a combination drug, respectively. Missing relationship will be considered as "Related". Summaries similar to those for the "all causality AEs" will be provided.

Grade II or above Diarrhea

Number of days of Grade II or above diarrhea will be summarized. For patients who had a Grade II or above diarrhea TEAE ongoing at the time of analysis, the duration of TEAE will be censored at data cutoff or safety follow-up completion date, whichever is earlier. The safety follow-up completion date is the defined as the earlier day of the last treatment plus 30 days and death day (if applicable).

Serious AE and Death

Treatment-emergent SAEs and treatment-related SAEs will be summarized by MedDRA SOC and PT and Maximum CTCAE grade.

Patients who experienced an SAE during the AE reporting period will be listed for all safety patients.

Deaths that occur on the same day or after the first dose of study treatment and within 30 days of the last dose of any study treatment will be summarized. The number and percentage of patients who died during the study treatment and within 30 days after the last dose will be presented.

A listing of death data will include all deaths that occurred during the reporting period for deaths, which starts from the signing of informed consent to the end of the follow-up period. The listing will include date of death, and the number of days relative to the administration of the first and last dose.

Adverse Events of Clinical Relevance

Selected AEs were pre-specified for additional focus due to the potential clinical significance of the event and/or the potential association with the investigational product. These events include those in the standard MedDRA (narrow or broad, as noted) query terms of: non-infectious diarrhea (broad SMQ), gastrointestinal haemorrhage (narrow SMQ), gastrointestinal obstruction (narrow SMQ), acute kidney injury (narrow acute renal failure SMQ) and preferred term of ventricular fibrillation and ventricular tachycardia. Tables listing the incidence, maximum severity and drug relationship of these events in the safety population will be generated.

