### 10.8 Analysis and Sample size for sub-cohorts

Each sub-cohort will be analyzed for number of days of Grade II/III diarrhea and % treatment compliance achieved during the first two cycles. The % treatment compliance will be calculated as the number of capsules actually ingested over the number of capsules that should have been ingested per dose level multiplied by 100. The research questions addressed by sub-cohorts are hypothesis-generating and exploratory in nature. Initially 6 subjects will be assigned to each sub-cohort to assess the effect of intervention. Selected sub-cohorts will be extended to enroll up additional 20 patients. The decision of extending the enrollment will be based on clinical assessment without formal statistical testing. However, 20 patients will give 80% power to detect 20% difference in % treatment compliance between two arms and 57% power to detect the difference of 25% in the number of days of having Grade II/III diarrhea using two-sided Z test with pooled variance at type I error rate of 0.15. The control rates assumed are 70% for treatment compliance and 30% for diarrhea. The patients will be sequentially allocated to different sub-cohorts by the Sponsor to avoid section bias.

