combination arm, patients assigned to sub-cohorts IA and IB would receive napabucasin at 240 mg twice daily (480 mg total daily dose) starting on Day 1 of Cycle 1. Intra-patient dose escalation of napabucasin to 480 mg twice daily (960 mg total daily dose) was allowed for patients in these cohorts as tolerated. Patients assigned to sub-cohorts IIA and IIB would receive napabucasin at 480 mg twice daily (960 mg total daily dose) starting on Day 1 of Cycle 1. In the event of toxicity, dose adjustment of napabucasin was permitted, as recommended in dose modification guidelines. Additionally, patients assigned to sub-cohorts IA and IIA would receive prophylactic anti-diarrheal treatment starting the day prior to Day 1 of Cycle 1. Patients assigned to sub-cohorts IB and IIB would receive anti-diarrheal treatment on an as-needed basis starting with development of diarrhea (ie, any occurrence greater than the patient's baseline). For each combination regimen, patients would be sequentially assigned to each of the 4 sub-cohorts in the following order until 6 patients were accrued in each of the sub-cohorts: IA, IB, IIA, and IIB. If required, up to an additional 20 patients might be assigned to selected sub-cohorts to validate the observations in the initial 6 patients.

Sub-cohort	Napabucasin Starting Dose Level	Anti-diarrheal Administration*
IA	240 mg bid (480 total daily dose) ¹	Prophylactic
IB	240 mg bid (480 total daily dose) ¹	As needed
IIA	480 mg bid (960 total daily dose) ²	Prophylactic
IIB	480 mg bid (960 total daily dose) ²	As needed

Table 1 Tolerability Analysis of Napabucasin

¹Intra-patient dose escalation of napabucasin to 480 mg po twice daily (960 mg total daily dose) is allowed as tolerated. ²In case of toxicity, dose adjustment of napabucasin is permitted.

*See protocol amendment 2 [5] section 7.1.4 for details

A study cycle would consist of 28 days of daily administration of napabucasin in combination with cetuximab or panitumumab, or capecitabine. Cycles would continue until unacceptable toxicity, disease progression (clinical or radiological) or another discontinuation criterion is met. Pharmacokinetic (PK) assessments would be performed on the first 6 patients enrolled in each combination arm. Pharmacodynamic assessments would be performed in patients with readily accessible tumor tissue through an optional tumor biopsy. Evaluation of anti-tumor activity would be performed at 8-week intervals per RECIST 1.1 while patients remain on study.

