Daily treatment compliance will be reported for each patient by dose level cohort.

- The % of days the patient received full daily dose of napabucasin or higher out of actual treatment duration in days.
- The % of days the patient received a non-zero dose of napabucasin out of actual treatment duration in days.
- The % of days the patient received full daily dose of napabucasin or higher out of the first 56 days from treatment start.
- The % of days the patient received a non-zero dose of napabucasin out of the first 56 days from treatment start.

Daily treatment compliance will be grouped according to the following categories: < 60%, $\geq 60\% - < 80\%$, $\geq 80\% - < 90\%$, $\geq 90\%$, and will be summarized for all arms.

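### SAP 8.2.4.1 does not carry over the protocol's two-cycle window for diarrhea days and has no exposure adjustment, so the sub-cohort count can be confounded with time on treatment

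*SAP*

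**What the plan says.** Protocol 10.8, repeated in the synopsis, sets the sub-cohort analysis: "Each sub-cohort will be analyzed for number of days of Grade II/III diarrhea and % treatment compliance achieved during the first two cycles".

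SAP 8.2.4.1, under its diarrhea item, says: "Number of days of Grade II or above diarrhea will be summarized". No time window follows. For an episode still ongoing at analysis, "the duration of TEAE will be censored at data cutoff or safety follow-up completion date, whichever is earlier". Safety follow-up completion is the last treatment day plus 30 days, or death if that comes first. The treatment-emergent definition in the same section likewise extends "up to 30 days after the last dose of any study drug". No rate per day on treatment is given. Under SAP 8.2, data are generally summarized by arm and sub-cohort.

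The SAP's treatment of compliance, the companion measure in Protocol 10.8, is mixed (SAP 8.2.1). The overall napabucasin formula, cumulative actual dose over planned dose, has no two-cycle window either. Of the four daily compliance measures, two are taken over actual treatment duration and two over 56 days, for example: "The % of days the patient received full daily dose of napabucasin or higher out of the first 56 days from treatment start". SAP 2.1 gives the cycle length: "A study cycle would consist of 28 days of daily administration of napabucasin". Two cycles are therefore 56 days.

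**The concern.** Comparing the two starting-dose regimens, and prophylactic with as-needed anti-diarrheal treatment, is a secondary objective (Protocol 2.2, SAP 2.1.2). Days of diarrhea is one of the two measures that Protocol 10.8 names for it.

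A count of days grows with the days over which it is taken. With a common window, patients treated for at least two cycles are counted over the same 56 days. Without one, each patient contributes as many days as treatment and follow-up last. If one regimen keeps patients on drug longer, it collects more diarrhea days even when the risk on any given day is the same or lower.

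Later days also say less about the contrasts of interest. The groups starting at 240 mg may escalate to 480 mg (Protocol 4.1, 4.3), and anti-diarrheal treatment may be adjusted in all four sub-cohorts (Protocol 7.1.4).

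**Working it through.** **1. The plan's own figure.** Protocol 10.8 states 57% power for diarrhea. Its inputs are a control rate of 30%, a difference of 25 points, a two-sided Z test with pooled variance, type I error 0.15, and 20 patients, read here as 20 per group.

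- Mean rate = (0.30 + 0.55)/2 = 0.425
- Standard error under no difference = sqrt(2 × 0.425 × 0.575/20) = 0.156
- Standard error under the alternative = sqrt((0.30 × 0.70 + 0.55 × 0.45)/20) = 0.151
- Power = Φ((0.25 − 1.44 × 0.156)/0.151) = 56.6%

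The 57% reproduces for an increase from 30% to 55%. A decrease from 30% to 5% would give 75.1%. The protocol therefore handled diarrhea as a proportion. It does not say whether of days or of patients. If of days over two cycles, the target difference is 0.25 × 56 = 14 days.

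**2. Effect of the window.** Let q be the share of days with Grade II or above diarrhea and D the days on treatment.

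- No window: expected days = q × D
- Windowed: expected days = q × min(D, 56)

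The durations lie in the 4 to 16 weeks that Protocol 4.6 expects for most patients. The rate q is an assumption, taken as constant over time and equal in both groups. Days after the last dose are left out.

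| q | No window, 8 vs 16 weeks | First 56 days, 8 vs 16 weeks | First 56 days, 4 vs 8 weeks |
|---|---|---|---|
| 5% | 2.8 vs 5.6 | 2.8 vs 2.8 | 1.4 vs 2.8 |
| 10% | 5.6 vs 11.2 | 5.6 vs 5.6 | 2.8 vs 5.6 |
| 30% | 16.8 vs 33.6 | 16.8 vs 16.8 | 8.4 vs 16.8 |

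At q = 30%, the protocol's control rate if read as a share of days, the gap without a window is 33.6 − 16.8 = 16.8 days. That exceeds the 14-day target difference, although the daily rate is the same in both groups.

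**3. The order can reverse.** Regimen 1: 10% of days for 16 weeks, 0.10 × 112 = 11.2 days. Regimen 2: 15% of days for 8 weeks, 0.15 × 56 = 8.4 days. Without a window, the regimen with the lower daily rate looks worse. Within 56 days the counts are 0.10 × 56 = 5.6 and 0.15 × 56 = 8.4, in the right order.

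**4. What the window leaves.** The last column shows that stopping before day 56 still lowers the count. Dividing by days on treatment within the window removes this: 2.8/28 = 10% and 5.6/56 = 10%.

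**The case against.** The SAP never says that it counts over all exposure. It is silent on the window, and its introduction tells the reader to use it together with the protocol, so the protocol's window is not expressly withdrawn. The censoring sentence only closes episodes that are still ongoing. This stands in part: counting over all exposure is an inference. But every rule the SAP does give runs past the end of cycle 2, and nothing stops the count at day 56.

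The two-cycle phrase in Protocol 10.8 could grammatically belong to compliance alone. Since one sentence names both measures, the joint reading is the more natural one. If the sponsor meant otherwise, the SAP should say so.

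A reader might infer that the SAP singled out diarrhea when it dropped the window. The documents do not support that, because the overall compliance formula lacks the window too.

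A reader might also set 4 against 16 weeks and infer a four-fold distortion (at 10%, 2.8 versus 11.2 days). Those are the ends of the range expected across most individual patients, not the averages of two regimens. Under a 56-day cap, 2.8 versus 5.6 would remain, so half of that ratio is not due to the missing window.

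The constant daily rate is also open to challenge. Protocol 1.4 describes Grade 3 diarrhea as transient, and Protocol 7.1.4 and 7.2.4 allow adjustment of anti-diarrheal treatment and of BBI608 when events are poorly controlled. Late days may carry less diarrhea, which would shrink the gaps. This stands.

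Finally, Protocol 2.2 says tolerability is judged on adverse events and the dose intensity reached, and the SAP analyzes both. It also defines treatment duration in its exposure section, which would help a reader interpret a raw count. This limits the consequence but leaves the named measure without its window.

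**Conclusion.** The point holds as a mismatch that should be corrected. The protocol's two-cycle window for diarrhea days is absent from SAP 8.2.4.1, and no exposure adjustment takes its place. Followed as written, the SAP gives a raw count that is confounded with exposure if sub-cohorts differ in time on treatment.

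The size depends on that difference. With a constant and equal daily rate, doubling treatment from 8 to 16 weeks doubles the expected count without a window and leaves it unchanged within 56 days. Rates and durations are illustrative.

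It is tempting to conclude that the analysis is biased against the better-tolerated regimen. The documents do not establish this. No section shows that time on treatment differs between sub-cohorts, and treatment also ends for progression (Protocol 5.6), so longer treatment need not mean better tolerability. The direction is a possibility, other things equal.

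The sub-cohort questions are exploratory, start with 6 patients each and carry no formal test for extension. The primary endpoint, disease control rate, is not affected.

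**What to change.** In SAP 8.2.4.1:

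- Define the sub-cohort endpoint as the number of days with Grade II or above diarrhea within days 1-56 from first dose, with episodes truncated at day 56.
- Report it as a count and as a percentage of days on treatment within that window, with numerator and denominator of the percentage covering the same days.
- Keep the count without a window as a supportive summary.
- State that the grade range changes from Grade II/III in Protocol 10.8 to Grade II or above, and why.

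The cost is a few sentences in the SAP and one derived variable. The data are already collected: adverse event dates and grades, and dosing dates.

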8.2.4.2. Laboratory Data

For the purposes of summarization in both the tables and listings, all laboratory values will be converted to standardized units. If a laboratory value is reported using a non-numeric qualifier (eg, less than [<] a certain value, or greater than [>] a certain value), the given numeric value will be used in the summary statistics, ignoring the non-numeric qualifier.

Laboratory test results will be summarized according to the scheduled sample collection time point. Change from baseline will also be presented. Unscheduled laboratory test results will be listed and included in laboratory shift tables. The parameters to be analyzed follow:

- Hematology: CBC including hemoglobin, hematocrit, white blood cell count with 5-part differential, red blood cell, and platelet count.
- Blood chemistry: CO₂, calcium, phosphorus, magnesium, albumin, glucose, serum creatinine, lactate dehydrogenase (LDH), uric acid, blood urea nitrogen (BUN), AST, ALT, alkaline phosphatase, total and direct bilirubin, and total protein, sodium, potassium, and chloride.

Shift tables will be constructed for laboratory parameters to tabulate changes in NCI CTCAE for toxicity (version 4.0) from baseline to post baseline worst CTC grade. Parameters to be tabulated will include:

- Hematology: ALC, ANC, hemoglobin, platelet count, WBC
- Serum chemistry: ALT, AST, alkaline phosphatase, creatinine, total bilirubin, calcium, magnesium, potassium, sodium, and phosphate.

Summary statistics will also be presented for shift from baseline urinalysis values.

• Urinalysis: protein, specific gravity, glucose, and blood.

By-patient listings to be presented include hematology, serum chemistry, and urinalysis results.

A listing of all laboratory parameters, including hematology, biochemistry, and urinalysis, will be provided, including the test result, units, normal range (H and L) and change from baseline, and CTCAE grades (if available). Patients who developed toxicities of Grade \geq 3 will also be listed.

Figures of maximum post-baseline vs baseline values will be produced for key lab parameters, including but not limited to ANC, platelets, and liver function tests (ALT/SGPT, AST/SGOT, alkaline phosphatase, and total bilirubin) as well as E-DISH scatter plots.

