# 3.1 Inclusion Criteria

Each patient must meet the following criteria to be enrolled in this study.

1. Signed written informed consent must be obtained and documented according to International Conference on Harmonization (ICH), Good Clinical Practice (GCP), the local regulatory

requirements, and permission to use private health information in accordance with the Health Insurance Portability and Accountability Act (HIPPA) prior to study-specific screening procedures.

- 2. A histologically or cytologically confirmed colorectal cancer that is metastatic, unresectable, or recurrent.
- 3. Patients must have received at least 2 regimens containing 5-FU, oxaliplatin, or irinotecan.
- 4. Patients to be enrolled in the Cetuximab or Panitumumab combination arms must have colorectal cancer which is K-Ras wild-type.
- 5.  $\geq$  18 years of age.
- 6. Measurable disease as defined by Response Evaluation Criteria in Solid Tumors (RECIST 1.1, see Section 9).
- 7. Karnofsky performance Status  $\geq$  70% (Section 15).
- 8. Male or female patients of child-producing potential must agree to use contraception or avoidance of pregnancy measures during the study and for 30 days after the last BBI608 dose.
- 9. Females of childbearing potential must have a negative serum pregnancy test.
- 10. Aspartate transaminase (AST) and alanine transaminase (ALT)  $\leq$ 2.5 × upper limit of normal (ULN), or  $\leq$  3.5 × ULN with metastatic liver disease.
- 11. Hemoglobin (Hgb)  $\geq$  10 g/dl.
- 12. Total bilirubin  $\leq 1.5 \times ULN$ .
- 13. Creatinine ≤ 1.5 × ULN or creatinine clearance > 60 mL/min/1.73 m² for patients with creatinine levels above institutional normal.
- 14. Absolute neutrophil count  $\geq 1.5 \times 10^9/L$ .
- 15. Platelets  $\geq 100 \times 10^9 / L$ .
- 16. Life expectancy  $\geq$  3 months.

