# 4.5 Dose-Limiting Toxicity

Dose-limiting toxicity is defined by the occurrence of any of the following toxicities possibly or probably related to BBI608 in combination with Cetuximab, or Panitumumab or Capecitabine within 28 days of treatment. DLT will be scored during the 28 days of BBI608 treatment.

- Grade 4 hematological toxicity
- Grade 3 or 4 non-hematological toxicity, except:
  - o Grade 3 or 4 nausea/vomiting/anorexia, diarrhea and fatigue will be considered a DLT only if it persists more than three (3) days despite optimal medical management
  - o Alopecia will not be considered a DLT

Adverse events considered related to Cetuximab, or Panitumumab or Capecitabine will not be considered DLTs.

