# 5.3.3.2 Week 2 (Cycle 1, Day 8)

- Karnofsky performance status
- Vital signs (weight, pulse)
- Hematology (see Section 6.3)
- Blood chemistry (see Section 6.3)
- Liver function tests (see Section 6.3)
- Electrolytes (see Section 6.3)
- Urinalysis (see Section 6.3)
- Assess AEs
- Tumor biopsy, if applicable (see Section 6.5.1)
- Record concomitant medication
- The second dose of BBI608 will be given approximately 12 hours after the first dose.
- Blood samples for pharmacokinetics, (for only the first six patients enrolled in this arm.)
- Dispense BBI608 (one week supply)
- Dispense Capecitabine (two week supply)

Blood samples for pharmacokinetics will be collected immediately prior to the first dose of BBI608 and will continue through 24 hours after administration of the first dose of BBI608. Specific details for the collection of blood samples for pharmacokinetics can be located in Sections 6.4 and Section 16.

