## 7.2.3 Capecitabine

## Hematological:

ANC (x10  /L)		Platelets (x10  /L)	1st Event Dose	2nd Event Dose	3rd Event Dose	4th Event Dose
≥ 1.5	and	≥ 75	100%	100%	100%	100%
1-1.49	or	50-74.9	delay* then 100%	delay* then 75%	delay* then 50%	discontinue
0.5 - 099	or	25 - 49.9	delay* then 75%	delay* then 50%	discontinue	discontinue
< 0.5	or	< 25	discontinue or delay* then 50%	discontinue	discontinue	discontinue

\* delay until ANC ≥ 1.5x10^9/L and platelets ≥ 75 x10^9/L

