- Hematopoietic growth factors, including filgrastim (Neupogen®), or other granulocyte colony stimulating factors (G-CSF), are permitted following documented and clinically significant neutropenia after the patient has completed at least one cycle of treatment with BBI608
- Prophylactic antiemetics may be administered according to standard practice
- Megestrol acetate (Megace®)
- Dethamethasone
- Diphenhydramine
- Cimetidine
- Ranitidine

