7.2. Definition of Baseline Values

Unless otherwise specified, the baseline value is defined as the value collected at the time closest to, but on or prior to, the start of study drug administration. CT and MRI scans may be considered for baseline assessment only if they were performed within 30 days of the first dose of napabucasin.

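### For ANC and platelets the planned laboratory figures plot the highest post-baseline count, so a transient fall, or a fall after a normal first on-treatment count, will not show in them

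*SAP*

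**What the plan says.** SAP 8.2.4.2 (Laboratory Data) states: "Figures of maximum post-baseline vs baseline values will be produced for key lab parameters, including but not limited to ANC, platelets". The sentence goes on to ALT, AST, alkaline phosphatase and total bilirubin, and ends with E-DISH scatter plots. One statistic, the maximum, governs every parameter named. Nowhere does the SAP substitute a minimum or worst value for blood counts.

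Baseline is defined in SAP 7.2 as "the value collected at the time closest to, but on or prior to, the start of study drug administration", so any count taken after BBI608 has started is eligible to be the plotted maximum.

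The protocol consistently treats a low count as the harm:

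- Section 3.1 sets entry floors: "Absolute neutrophil count" of at least 1.5 x10^9/L and platelets of at least 100 x10^9/L.
- Section 4.5 makes "Grade 4 hematological toxicity" a dose-limiting toxicity.
- The haematological table in Section 7.2.3 (Capecitabine) is driven by falling counts, down to ANC below 0.5 or platelets below 25. Its footnote reads "delay until ANC" and platelets are back at or above 1.5 and 75.
- Section 7.6.1 makes growth factor use conditional on "documented and clinically significant neutropenia".

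**The concern.** A plot of post-baseline extreme against baseline is meant to show at a glance which patients moved in the harmful direction. For the liver tests the maximum does that. For ANC and platelets it shows each patient's best count, which is often a recovery or an early unaffected value.

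The rest of the SAP's safety section respects direction. The shift tables in 8.2.4.2 use the worst post-baseline grade, 8.2.4.3 uses the worst post-baseline ECG result, and 8.2.4.4 reports both the maximum increase and the maximum decrease for vital signs. The figure sentence is the exception, which suggests a drafting slip and not a choice.

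Safety is part of the primary objective, and these are the only laboratory figures of post-baseline extremes that the SAP specifies for counts. Followed literally, they do not do their job for those two parameters. The alternative is that the programmer quietly plots something else, which would be an undocumented departure from the SAP.

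**Working it through.** The plan gives no figure to reproduce here. The check compares the plotted statistic with the direction of harm and the sampling schedule, and then works through an illustration.

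**1. Direction.** If a patient's post-baseline counts are x1, ..., xn, the figure plots max(x1, ..., xn). The harm lies in min(x1, ..., xn). The maximum is low only if every xi is low.

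**2. Schedule.** The maximum can never be below the first on-treatment count. In all three arms, that count is scheduled for the day the combination drug is first given: Day 5 for cetuximab, Day 8 for panitumumab and Day 8 for capecitabine (Protocol 5.3.1 to 5.3.3). The capecitabine Day 8 visit includes "Dispense Capecitabine (two week supply)", so the Day 8 count reflects about a week of BBI608 alone. Protocol 4.3 reports no bone marrow suppression with BBI608 in phase I, so this count should be close to baseline. It then acts as a floor, and no later fall on capecitabine can move the plotted point below it.

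**3. Hand example** (assumed capecitabine-arm ANC values, x10^9/L; visit days from Protocol 5.3.3):

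| Visit | ANC |
|---|---|
| Baseline | 4.0 |
| Cycle 1 Day 8 | 3.8 |
| Cycle 1 Day 15 | 1.2 |
| Cycle 1 Day 21 | 0.4 |
| Cycle 2 Day 1 | 2.0 |

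- Plotted under the SAP: max = 3.8, and 3.8 / 4.0 = 95% of baseline.
- Nadir: min = 0.4, which is 0.4 / 4.0 = 10% of baseline and lies in the protocol's lowest ANC row (below 0.5).

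**4. How general this is.** Assume counts of 4.0 x exp(e), with e normal, mean 0 and SD 0.25, and k of n readings cut by 85%. A cut reading is almost never the largest while an uncut one remains, so the median maximum is close to 4.0 x exp(0.25 x z), where z is the normal quantile at 0.5^(1/(n-k)).

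- n = 6, k = 0: 0.5^(1/6) = 0.891, z = 1.23, median maximum = 5.44.
- n = 6, k = 1: 0.5^(1/5) = 0.871, z = 1.13, median maximum = 5.30.
- n = 6, k = 5: one uncut reading, z = 0, median maximum = 4.0.
- n = 6, k = 6: all cut, 0.15 x 5.44 = 0.82.

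Simulation gives the same medians. The median minimum with n = 6 is 2.94 for k = 0 and 0.60 for k = 1. For n from 3 to 8 with one reading cut, the median maximum drops by only 0.1 to 0.3, while the median minimum goes from about 2.8 to 3.3 down to 0.6.

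The maximum is therefore nearly blind to a fall until every post-baseline reading is low, and at that point it does show it.

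**5. Growth factor.** Under Protocol 7.6.1, growth factors "are permitted following documented and clinically significant neutropenia after the patient has completed at least one cycle of treatment with BBI608". A treated patient could then have a raised later ANC, which would become the plotted maximum. This is a possibility and cannot be sized from the documents.

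**The case against.** The strongest reply is that nothing is hidden. SAP 8.2.4.2 also plans:

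- shift tables to worst post-baseline grade for ANC, platelets, lymphocytes, haemoglobin and white cells, with unscheduled results included;
- summaries and changes from baseline by scheduled time point;
- by-patient listings with grades;
- a listing of patients with toxicity of Grade 3 or above.

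SAP 8.2.4.1 tabulates adverse events by maximum grade, and 8.2.3.4 lists the DLTs. The arm-closure rule in 4.2.1 counts DLTs, no hypothesis is tested (4.1) and no formal interim analysis is planned (5). No decision rests on these figures. All of this stands, and it limits the point to presentation.

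It can also be said that the simulation shows little beyond its own construction: when the uncut readings set the maximum, the maximum naturally barely moves. That is fair. The simulation illustrates the property of the statistic and measures nothing about this trial. Marked myelosuppression is also hypothetical for BBI608 itself, although the capecitabine dose table does provide for low counts.

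A reader might infer two stronger things. One is that neutropenia and thrombocytopenia can never appear in these figures. They can: a patient whose only post-baseline count is low, or whose counts all stay low, plots low. The other is that the figures would contradict the shift tables. They would not, because a maximum and a worst grade are different summaries of the same data and both can be true.

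None of these replies makes the maximum the right statistic for a count whose toxicity is a fall. Leaving the parameter list open widens what is plotted but does not change the statistic.

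**Conclusion.** The point holds as a minor error confined to the figures. For ANC and platelets, the stated rule plots the uninformative end, so a transient fall, or a fall after a normal first on-treatment count, will not show. The figures fail their safety purpose for counts, but no safety data are lost, because cytopenia is reported in the other outputs. It would be going too far to read this as concealment of myelosuppression or as a threat to the trial's safety conclusions.

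The direction of harm and the wording of the figure sentence come straight from the documents. The numerical illustrations rest on assumed counts: a baseline ANC of 4.0, SD 0.25 on the log scale, 3 to 8 readings and an 85% fall. The remark about the first on-treatment count also relies on the phase I observation that BBI608 alone does not depress counts.

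**What to change.** Amend the figure sentence in SAP 8.2.4.2 so that the statistic follows the toxic direction:

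- minimum post-baseline against baseline for ANC and platelets, and for any other plotted parameter whose toxicity is a decrease;
- maximum post-baseline against baseline for ALT, AST, alkaline phosphatase and total bilirubin.

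Keep the open-ended parameter list and the E-DISH scatter plots as they are. There is no need to add parameters that the sentence does not name now; the rule simply has to cover them if they are plotted.

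The cost is one sentence in the SAP and a per-parameter choice of minimum or maximum in the figure program, with matching axis labels. No new data are needed and no other output changes.
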